6.2.7.2 Supportive Secondary Efficacy Analyses

6.2.7.2.1 Analyses of Total Number of MAHE

The total number of MAHE in [Section 5.1.3.1](#) will be analyzed to compare trilaciclib and placebo using a negative binomial regression model to account for the potential over-dispersion. The model includes the stratification factors of ECOG (0 or 1 vs. 2) and brain metastases (Yes vs. No), and treatment as a fixed effect. The logarithm transformation of duration of induction treatment period divided by 7 (i.e. week) will be included as an offset variable in the modeling. The two-sided p-value, aRR (trilaciclib vs placebo) and its 95% CIs will be presented.

The total number of MAHE will be summarized descriptively, along with the weeks of induction treatment duration, and the event rate per week (calculated as the total number of events/duration of induction treatment period divided by 7 [i.e. week]). The cumulative incidence of events during the induction treatment period will be summarized and presented graphically in three-week intervals.

The total number of individual MAHE components (specified in [Table 4](#)) will be summarized similarly, except that DSN > 5 days will be summarized cumulatively by cycle instead of three week intervals, and the offset will be the logarithm transformation of number of induction cycles divided instead of duration of induction treatment period.

Time-to-first MAHE endpoints (overall and individually) in [Section 5.1.3.1](#) will be summarized similar to DSN, Strategy 2 as described in [Section 6.2.7.1.5](#). A graphical display of cumulative incidence will also be presented.

An event chart of the induction treatment period will also be included, with horizontal bars for each subject's cycle length and time on the x-axis, with points plotted for each of the MAHE components.

6.2.7.2.2 Analyses of Objective Response

The patients in each category of TPR according to the investigator tumor assessment (CR, PR, SD, PD, or NE) will be presented in a data listing. The number and percentage of patients in each category of BOR (Confirmed CR, Confirmed PR, SD, PD, or NE), ORR, ORR_{UNCONFIRMED} and CBR according to the investigator tumor assessment (Confirmed CR, Confirmed PR, SD, PD, or NE) will be summarized. Detailed information of deriving tumor relevant responses is provided in [Section 5.1.3.2.4](#).

Similar analyses will be repeated based on the derived responses according to the RECIST Version 1.1.

Estimates of response rate, along with its associated exact 95% two-sided CIs using Clopper-Pearson method will be computed for ORR and CBR within each treatment group.

The binary endpoint (Yes, No) of ORR for the two treatments (trilaciclib and placebo) will be analyzed to compare trilaciclib and placebo using stratum-adjusted method to account for the stratification factors. The adjusted proportion difference (trilaciclib vs placebo) and its 95% CIs will be calculated using CMH weight outlined in Kim et al. 2013. The two-sided p-value will be calculated using stratified exact CMH method.

The analyses are based on the response evaluable analysis set. The supportive data listings will also be provided.

Subsets based on subjects with and without dose reductions will also be included.

A waterfall plot showing the best % change in target lesion sum will also be included.

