## **13.2. General Considerations**

### **13.2.1. Analysis Sets**

The intent-to-treat (ITT) analysis set includes all randomized patients. Analyses using the ITT will be conducted on the basis of the assigned treatment. All efficacy analyses will be assessed using the ITT and the ITT is the primary analysis set for analysis. A modified ITT (mITT) analysis set is a subset of the ITT analysis set and will only include the ITT patients who received at least 1 dose of study drug. Supportive sensitivity analyses will be conducted based on the mITT analysis set for primary and key secondary efficacy endpoints to evaluate the robustness of the results. Analyses using the mITT will be conducted on the basis of the assigned treatment.

The safety analysis set includes all enrolled patients who received at least 1 dose of study drug. The safety analysis set analyses will be conducted on the basis of the actual treatment received. All safety analyses will be assessed using the safety analysis set.

A per-protocol (PP) analysis set is a subset of the mITT analysis set and may also be used to analyze select endpoints; it will be based on study drug exposure (compliance and/or time on study drug) and major protocol deviations, which will be fully defined and documented before unblinding. The criteria for inclusion in the PP analysis set will be finalized and documented prior to unblinding patients in the study.

The response evaluable analysis set will include all patients who are in the mITT and have at least 1 postbaseline tumor assessment, or have clinical progression as noted by the investigator before their first postbaseline tumor scan or have died due to disease progression before their first postbaseline tumor scan. The response evaluable analysis set will be used for analyses of tumor response.

The PK set will include all dosed patients in Part 1 with evaluable PK data.

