3.1.1. Intent-to-Treat Analysis Set

The intent-to-treat (ITT) analysis set includes all randomized patients. Analyses using the ITT will be conducted on the basis of the assigned treatment. The ITT is the primary analysis set for all efficacy analysis.

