3.1.5. Response Evaluable Analysis Set

The Response Evaluable Analysis Set will include all patients who are in the mITT and (1) have at least 1 post-baseline tumor assessment, (2) discontinued treatment because of clinical progression, or (3) died due to disease progression before their first postbaseline tumor scan. The response evaluable analysis set will be used for analyses of tumor response.

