3.2. Protocol Deviations

Certain protocol deviations are key in that they may affect the ability to assess the safety and efficacy of study drug. Patients with key deviations will be excluded from the PP analysis set. All patients who meet the definition of the ITT/mITT analysis sets will be included in the ITT/mITT analysis set regardless of these deviations.

The criteria for inclusion in the PP set will be finalized and documented prior to unblinding patients for the study.

If a patient is randomized, but fails to receive treatment, the reason for not receiving treatment will be noted in the CSR. Any such patients who are not treated will be excluded from the mITT, safety, response evaluable, and PP analysis sets but will be included in the ITT and in the patient listings for the CSR.

If the wrong treatment is administered to a patient, and the reason for the incorrect treatment is documented, this will be noted in the CSR and the patient's data included in the Safety Analysis Set based on the actual treatment received. All major protocol deviations will be reviewed in a data review meeting to classify protocol deviations as non-key or key, and to discuss the potential impact on statistical analysis. This will be documented in a note to file prior to database lock and unblinding.

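### The between-arm ORR comparison rests on the response evaluable set, with no ITT counterpart named, although both documents make ITT the set for all efficacy analyses

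*SAP*

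**What the plan says.** On the general rule the two documents agree. SAP 3.1.1: "The ITT is the primary analysis set for all efficacy analysis". Protocol 13.2.1: "All efficacy analyses will be assessed using the ITT and the ITT is the primary analysis set for analysis".

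Both then assign tumour response elsewhere. SAP 3.1.5: "The response evaluable analysis set will be used for analyses of tumor response"; Protocol 13.2.1 has an equivalent sentence. SAP 6.2.7.2.2 applies this to ORR, with a CMH-weighted difference between arms and its 95% CI. "The two-sided p-value will be calculated using stratified exact CMH method". The set is then named: "The analyses are based on the response evaluable analysis set".

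To enter the set under SAP 3.1.5, a patient must be in the mITT set (at least one dose) and must "have at least 1 post-baseline tumor assessment", or qualify by one of two other routes: "2) discontinued treatment because of clinical progression, or (3) died due to disease progression before their first postbaseline tumor scan". SAP 3.2 adds, for patients randomised but never treated: "Any such patients who are not treated will be excluded from the mITT, safety, response evaluable, and PP analysis sets".

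The repeat analyses on mITT and PP in SAP 6.2.7.1.5 cover only the primary and key secondary endpoints. SAP 6.2.7.2.3 places PFS on ITT.

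**The concern.** A between-arm p-value is protected by randomisation only if everyone randomised is counted. Here the denominator depends on what happens after randomisation, and two patients with the same lack of response data can be treated differently. One who progresses clinically and stops, or dies of progression, without a scan counts as a failure. One who dies of infection, or withdraws and is never scanned, is not counted at all.

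Trilaciclib is intended to reduce chemotherapy toxicity, so losses of the second kind may differ by arm. ORR would then differ between arms even if the same number of randomised patients responded. ORR and PFS, both listed as antitumour endpoints, would also be compared on different populations, and no ITT result for ORR is planned to show whether the choice mattered.

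**Working it through.** **Who leaves the denominator.** Reading SAP 3.1.5 and 3.2 with Protocol 12.3 and note l1 to Table 9-1:

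| Patient | In the response evaluable set? |
|---|---|
| Dosed, any post-baseline scan, on or off treatment | Yes |
| Dosed, no scan, stopped for clinical progression | Yes, as non-responder |
| Dosed, no scan, died of progression | Yes, as non-responder |
| Dosed, stopped for toxicity, scanned later | Yes |
| Dosed, withdrew or stopped for toxicity, never scanned | No |
| Dosed, died of another cause before any scan | No |
| Randomised, never dosed | No |

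The fourth row matters. Patients who stop for reasons other than progression continue to have CT or MRI about every 2 months (Protocol 12.3), and scans are scheduled at the 30- and 90-day visits for those who have not progressed (Table 9-1, note l1). Stopping for toxicity therefore does not by itself exclude a patient.

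**Size.** The plan gives no ORR assumption, power or expected number of exclusions, so it has no ORR figure to reproduce. The inputs are:

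- Patients per arm: 53. SAP 2.3 needs 50 evaluable per arm at 95% evaluability; 50/0.95 = 52.6, rounded up to 53, or 106 in total as stated. SAP 2.3 also speaks of about 100 patients; with 50 per arm each exclusion would weigh slightly more.
- Response rate: 50% to 60%, the background range in Protocol 4.1. This gives 26 or 32 responders of 53.
- Exclusions: assumed, 1 to 8 per arm. Dosed patients who are excluded have no scan and so cannot be responders; never-dosed patients are also taken as non-responders.
- The same number of ITT responders in each arm, so the ITT difference is zero.

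Formula: response evaluable ORR = r / (53 − e), where r is the number of responders and e the number excluded. The rise over ITT is r·e / [53·(53 − e)].

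| Excluded, trilaciclib / placebo | r = 26 per arm | Difference (points) | r = 32 per arm | Difference (points) |
|---|---|---|---|---|
| 0 / 0 (ITT) | 26/53 = 49.1% in both | 0 | 32/53 = 60.4% in both | 0 |
| 3 / 3 | 26/50 = 52.0% in both | 0 | 32/50 = 64.0% in both | 0 |
| 1 / 5 | 26/52 = 50.0% v 26/48 = 54.2% | −4.2 | 32/52 = 61.5% v 32/48 = 66.7% | −5.1 |
| 2 / 8 | 26/51 = 51.0% v 26/45 = 57.8% | −6.8 | 32/51 = 62.7% v 32/45 = 71.1% | −8.4 |

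Differences are trilaciclib minus placebo, from unrounded rates. Swapping the exclusions (5 / 1 and 8 / 2) reverses the signs.

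With three exclusions per arm, both rates rise by 26×3/(53×50) = 2.9 points or 32×3/(53×50) = 3.6 points, and the comparison is unaffected.

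**Against sampling error.** The standard error of the difference is √[2p(1 − p)/53], which is 9.7 points at 49.1% and 9.5 points at 60.4%. The 95% half-width is about 19 points (1.96 × 9.7 = 19.0; 1.96 × 9.5 = 18.6).

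**The case against.** The best answer is that nothing here is hidden or ambiguous. The set is specified in Protocol 13.2.1, SAP 3.1.5 and SAP 6.2.7.2.2, and a specific rule for tumour response would ordinarily override a general one. A programmer would know what to run. A reader who infers that the population was picked after the data were seen would be wrong: only membership is determined after randomisation. This stands, and it reduces the conflict between sections to loose wording. It does not supply an ITT comparison.

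A reader might also infer that every patient who stops early for toxicity is dropped. The continued scanning in Protocol 12.3 and Table 9-1 does not support that, and early progressors without a scan are kept. The excluded group may be small.

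A third tempting reading is that the randomised comparison is lost for the endpoint meant to show that trilaciclib does no harm. The documents give that role to OS (Protocol 13.5.2.1, SAP 5.1.2.4), which is analysed on ITT, as is PFS. ORR is a supportive secondary endpoint and is not among the five hypotheses in SAP 6.2.7.1.4.

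Finally, SAP 6.2.1 already plans a table of patients in each analysis set with reasons for exclusion, so a reader could rebuild a crude ITT rate. That would not give the stratified difference, interval or p-value. The absence of an ITT analysis can be stated only for the readable text, because the list of changes in SAP Section 7 is blacked out.

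**Conclusion.** The point holds as a modest one. The only between-arm ORR comparison named in the readable text uses a prespecified subset whose membership depends on post-randomisation events, while the general efficacy rule in both documents says ITT.

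Under the assumptions shown, an imbalance of 4 to 6 excluded patients gives a spurious difference of about 4 to 8 points. Balanced exclusions give none, though both rates are flattered. These shifts are well inside the sampling error of about 19 points, but they are systematic and avoidable.

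The exclusion counts are assumptions, and the documents do not support an inference that the set favours trilaciclib. If the drug reduced early losses, the larger exclusions would fall on placebo and its ORR would be the one raised.

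No claim in the testing procedure depends on ORR. The change is worth making because the remedy is cheap and puts ORR on the same population as PFS.

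**What to change.** 1. In SAP 6.2.7.2.2, base the between-arm ORR difference, CI and p-value on ITT. SAP 5.1.3.2.4 already codes a patient without a confirmed CR or PR as a non-responder, so no new imputation rule is needed. One added sentence should say that this includes patients with no post-baseline assessment, and that the same holds for the unconfirmed ORR.
2. Keep the response evaluable analysis as supportive, with one definition. Protocol 13.2.1 admits clinical progression noted by the investigator before the first scan; SAP 3.1.5 requires that treatment was discontinued for clinical progression; Protocol 11.1.3.3 counts a patient as evaluable only with a postdose scan. These should be aligned.
3. Reword SAP 3.1.1 so that the general rule and the supportive use of the response evaluable set agree.
4. Present the exclusion table in SAP 6.2.1 by arm and reason for this set.

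The cost is SAP wording and one extra table, with no new data collection. The reported ORR will be slightly lower in each arm, by an amount that depends on how many patients were excluded: about 3 to 4 points if it were three per arm.

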6.2.7.2.3 Analyses of DOR and PFS

The analysis method as described in [Section 6.2.7.1.3](#) for OS will be applied to PFS (derived) and DOR (investigator and derived), except DOR will exclude the Kaplan-Meier estimates for the survival rates at 3, 6, 9, and 12 months as well as the Cox proportional hazard model.

Spider plot by treatment group of % change in target lesion from baseline for each subject over time will be included based on derived assessments. Points will be included for best overall response (if CR or PR), new lesions, and end of treatment.

An event chart of the induction treatment period will also be included, with horizontal bars for each subject's cycle length and time on the x-axis, with points plotted for start and end of DOR.

For DOR, the analysis is based on the response evaluable analysis set; for PFS the analysis will be based on the ITT. The supportive data listings will also be provided.

6.2.7.2.4 Analyses of Hematology Lab Values

For the endpoints specified in [Section 5.1.3.4](#) and [5.1.3.5](#), in addition to descriptive statistics summary, graphical displays will be provided to facilitate evaluation of trends in the change in a given variable over time. Moreover, each of the ANC change over time analysis (i.e. observed value at windowed visit and cycle nadir) specified above will be done using three distinct data sets to evaluate the confounding effect of GCSF administration: all patients or cycles regardless of GCSF administration; inclusion of only those patients or cycles who had concurrent GCSF administration; and inclusion of only those patients or cycles who did NOT have concurrent GCSF administration. The "with" and "without" GCSF analyses are subsets of the total number of patients or cycles.

Figures of mean and 95% CI over time will be provided for ANC (with GCSF subsets also), platelet counts, HGB, change from baseline HGB, and ALC. Additionally, jitter scatter plots will be provided for mean and 95% CI by cycle for ANC nadir (with GCSF subsets also).

A Radar plot of grade 3/4 laboratory abnormalities during induction period, and during the first induction cycle will be presented.

6.2.7.2.5 Analyses of Other Binary Efficacy Endpoints

The following binary response variables (Yes, No) will be analyzed using the same method for occurrence of SVN except baseline ANC will not be a covariate in the modified Poisson model. See [Section 6.2.7.1.1](#):

- Occurrence of a Grade 3 or 4 hematologic toxicity during the induction treatment period (refer to [Section 5.1.3.3](#));
- Occurrence of an ESA administration during the induction treatment period (refer to [Section 5.1.3.6](#));
- Occurrence of an IV antibiotic administration during the induction treatment period (refer to [Section 5.1.3.7](#)); The offset in the modified Poisson model will be the logarithm transformation of duration of induction treatment period divided by 7 (i.e. week) instead of number of induction cycles. Additionally, total number of IV antibiotic administrations will be summarized descriptively.
- Occurrence of an infection SAE during the induction treatment period (refer to [Section 5.1.3.8](#)); The offset in the modified Poisson model will be the logarithm transformation of duration of induction treatment period divided by 7 (i.e. week) instead of number of induction cycles. Additionally, total number of infection SAEs will be summarized descriptively.
- Occurrence of a pulmonary infection SAE during the induction treatment period (refer to [Section 5.1.3.9](#)); The offset in the modified Poisson model will be the logarithm transformation of duration of induction treatment period divided by 7 (i.e. week) instead of number of induction cycles. Additionally, total number of pulmonary infection SAEs will be summarized descriptively.

[REDACTED]

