### Colony Stimulating Factors

**Patients will not receive colony stimulating factors (CSFs; eg, granulocyte colony stimulating factor [G-CSF]; granulocyte-macrophage colony-stimulating factor [GM-CSF]) or erythropoiesis stimulating agents (ESAs) during Induction Cycle 1 (ie, prior to the actual Cycle 2 Day 1 dosing visit).**

Although CSFs should not be routinely used as adjunctive treatment with antibiotic therapy for patients with fever and neutropenia in any cycle, they may be considered in patients with fever and neutropenia who are at high risk for infection-associated complications or who have prognostic factors predictive of poor clinical outcomes (including in Induction Cycle 1 if necessary). Subsequent use **after Induction Cycle 1** will be based on toxicities as outlined above. Please also refer to the ASCO guidelines ([Smith 2015](#)) for neutropenia.

When indicated, as outlined above in [Table 8-2](#) and [Table 8-3](#), either filgrastim or pegfilgrastim may be used per the prescribing information. In the event a patient has a neutropenic event requiring G-CSF in the subsequent cycle, then filgrastim or pegfilgrastim should not be initiated until at least 24 hours after dosing of the next subsequent cycle is complete (ie, no earlier than Day 4 of the next subsequent cycle). Filgrastim or pegfilgrastim should not be used to increase low neutrophil counts mid-cycle or prior to the start of the subsequent cycle.

For a hemoglobin level < 9.0 g/dL or symptomatic anemia when indicated, epoetin alfa or darbepoetin alfa may be used to treat patients per the prescribing information.

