#### 13.5.1.1. Methods of Analysis for Primary Myelosuppression Efficacy Endpoints

A 2-sided p-value will be calculated for the DSN in Cycle 1 using nonparametric analysis of covariance (ANCOVA) (Stokes 2012). The nonparametric ANCOVA will include study baseline ANC value as covariate, stratification factors of ECOG performance status (0 to 1 versus 2) and presence of brain metastases (yes versus no), and treatment as a fixed effect. Along with the descriptive statistics, the Hodges-Lehmann estimate of median difference between the 2 treatment groups, together with its 95% CIs will be provided.

The occurrence of severe (Grade 4) neutropenia is a binary response variable (yes versus no) and will be analysed to compare trilaciclib and placebo using modified Poisson regression (Zou 2004) to account for the variable duration of the induction treatment period for each patient. The model will include baseline value as covariate, the stratification factors of ECOG performance status (0 to 1 versus 2) and presence of brain metastases (yes versus no), and treatment as a fixed effect. The 1-sided p-value adjusted relative risk (aRR) (trilaciclib vs placebo) and its 95% CIs will be presented.

A detailed description of the analysis methods will be provided in the SAPs.

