#### 13.5.4. **Analysis of Supportive Secondary Efficacy Endpoints (Antitumor and Myelosuppression)**

The detailed derivation for these endpoints along with their analysis methods will be included in the SAPs.

For **Region 1 only**, OS will be considered as a supportive secondary endpoint and will be analyzed according to Section [13.5.2.1](#).

For **Region 2 only**, the composite MAHE endpoint will be considered a supportive secondary efficacy endpoint to be analyzed as described above (Section [13.5.3](#)).

All the remaining endpoints are relevant to both Regions.

Anti-tumor activity per Response Evaluation Criteria in Solid Tumors (RECIST 1.1) as assessed by the investigator will include the following:

- Objective response (CR or PR)
- Best overall response (BOR)
- Duration of objective response (DOR)
- Progression-free survival (PFS)

At each tumor assessment visit, an overall time point response by RECIST v1.1 will be determined programmatically using the information from target lesions, NTLs, and new lesions collected in the eCRF. BOR will be determined using visit responses until the last evaluable overall visit response prior to or on the date of (i) radiographic disease progression; (ii) withdrawal of consent to obtain scans; (iii) death; (iv) lost to follow-up; or (v) initiation of subsequent anticancer therapy, whichever is earlier.

Duration of Objective Response (DOR) is the time between first objective response of CR or PR and the first date that progressive disease is objectively documented or death, whichever comes first. Patients who do not experience objective CR or PR will not be included in the analysis. For patients with objective response of CR or PR but (i) withdrawal of consent to obtain scans; (ii) lost to follow up; (iii) initiation of subsequent anticancer therapy, or (iv) death, the DOR of this patient will be censored at the earliest date among these four.

PFS is defined as the time (number of months) from date of randomization until date of documented radiologic disease progression per RECIST version 1.1 or death due to any cause, whichever comes first. More specifically, PFS will be determined using all data until the last evaluable visit prior to or on the date of (i) radiographic disease progression per RECIST version 1.1; (ii) withdrawal of consent to obtain scans; or (iii) initiation of

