5.1.3.3. Occurrence of Grade 3 and 4 Hematologic Toxicities

Hematologic toxicities events are defined as any cycle where any hematologic lab value occurs that meets the CTCAE toxicity grade criteria for \geq Grade 3 and the value is treatment emergent. For details on which parameters are included and the definition of treatment emergent see [Section 5.2.4](#).

For the induction treatment period, the total number of hematologic toxicity events is the number of induction cycles in which there is at least one hematologic toxicity event. If a patient did not have any hematologic toxicity events, the value of 0 will be assigned to that patient. The number of induction cycles without hematologic toxicity events is calculated as total number of induction cycles received – total number of induction cycles with a hematologic toxicity event.

Therefore, any occurrence of a hematologic toxicity event during an induction cycle or the induction treatment period is defined as a binary variable (Yes or No); Yes if total number of induction cycles with a hematologic toxicity event ≥ 1 is observed, No for other scenarios.

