6.1.4. Adjustment for Covariates

Patient randomization was stratified by ECOG performance status (0 or 1 vs. 2) and presence of brain metastases (Yes vs. No). The efficacy analyses will use the stratification factors as covariates in statistical models.

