6.2.7.1 Primary and Key Secondary Efficacy Analyses

6.2.7.1.1 Primary Efficacy Analyses

The primary efficacy endpoint, occurrence of SVN, is a binary response variable (Yes, No). It will be summarized using descriptive statistics by treatment group and will be analyzed to compare trilaciclib and placebo using modified Poisson regression (Zou, 2004) to account for the variable duration of the induction treatment period for each patient. The model will include baseline ANC as a covariate, the stratification factors of ECOG (0 or 1 vs. 2) and brain metastases (Yes vs. No), and treatment as a fixed effect. The logarithm transformation of number of induction cycles will be included as an offset variable in the modeling. The two-sided p-value, adjusted rate ratio (aRR) (trilaciclib vs placebo) and its 95% CIs will be presented.

For the other primary efficacy endpoint, DSN in Cycle 1 based on Strategy 1 in [Section 5.1.1.2.1](#), treatment difference will be evaluated using a nonparametric analysis of covariance

(ANCOVA) (Stokes 2012). The nonparametric ANCOVA will include study baseline ANC value as covariate, stratification factors of ECOG (0 or 1 vs. 2) and brain metastases (Yes vs. No), and treatment as a fixed effect. A two-sided p-value will be generated from this model. Along with the descriptive statistics, the mean difference and Hodges-Lehmann estimate of median difference between the two treatment groups, together with its 95% CIs will be provided. Additionally, DSN for each cycle will be presented using descriptive statistics.

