6.2.7.1.2 Key Secondary Efficacy Analyses

Occurrence of RBC transfusions on/after 5 weeks on study is a binary variable and will be summarized using the same method for occurrence of SVN described in [Section 6.2.7.1.1](#) except baseline HGB will be used as a covariate instead of baseline ANC in the modified Poisson model. Also, the offset will be the logarithm transformation of duration of induction treatment period divided by 7 (i.e. week) instead of number of induction cycles, and. An additional sensitivity analysis will look all transfusions during the induction treatment period, and all transfusions with a subset of subjects completing at least 1 cycle.

Occurrence of GCSF administration is a binary variable and will be summarized using the same method for occurrence of SVN described in [Section 6.2.7.1.1](#).

All-cause dose reductions will be analyzed to compare trilaciclib and placebo using a negative binomial regression model to account for the potential over-dispersion. The model includes the stratification factors of ECOG (0 or 1 vs. 2) and brain metastases (Yes vs. No), and treatment as a fixed effect. The logarithm transformation of number of induction cycles will be included as an offset variable in the modeling. The two-sided p-value, aRR (trilaciclib vs placebo) and its 95% CIs will be presented.

The total number of all-cause dose reductions will be summarized descriptively, along with the number of induction cycles, and the event rate per cycle (calculated as the total number of events/total number of induction cycles). The cumulative incidence of events during the induction treatment period will be summarized and presented graphically by cycle.

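### The ESA administration model drops baseline ANC without putting baseline hemoglobin in its place, although the RBC transfusion model makes exactly that swap

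*SAP*

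**What the plan says.** SAP 6.2.7.1.1 analyses occurrence of severe neutropenia by modified Poisson regression with baseline ANC, the two stratification factors, treatment, and the log number of induction cycles as offset. Two key secondary binary endpoints inherit that model in SAP 6.2.7.1.2. G-CSF administration takes it unchanged, so it keeps baseline ANC. RBC transfusion on/after Week 5 takes it "except baseline HGB will be used as a covariate instead of baseline ANC in the modified Poisson model", with a different offset.

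SAP 6.2.7.2.5 then lists five supportive binary endpoints: Grade 3/4 hematologic toxicity, ESA administration, IV antibiotics, infection SAEs and pulmonary infection SAEs. These "will be analyzed using the same method for occurrence of SVN except baseline ANC will not be a covariate in the modified Poisson model". The section changes the offset for the last three, names no replacement covariate for any of them, and gives no reason.

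On ESA use, the protocol (8.4.5.2, Colony Stimulating Factors) says: "For a hemoglobin level < 9.0 g/dL or symptomatic anemia when indicated, epoetin alfa or darbepoetin alfa may be used".

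**The concern.** RBC transfusion and ESA administration are two responses to the same problem, anemia on chemotherapy. One model adjusts for baseline hemoglobin and the other adjusts for no blood count. The protocol's own thresholds make the difference hard to explain. Entry requires hemoglobin of at least 9.0 g/dL (Protocol 7.1.1), ESA use is linked to values below 9.0 g/dL, and transfusion to values below 8.0 g/dL (Protocol 8.7), each also allowed for symptomatic anemia. A patient who enters near the floor is closer to the ESA threshold than to the transfusion threshold. If baseline hemoglobin is worth having in the transfusion model, the case for it in the ESA model is at least as good.

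What is at stake is the width of one supportive interval. The comparison is inferential: the inherited method reports a p-value, an adjusted rate ratio and a 95% CI. A prognostic covariate that is already in the database could tighten that interval slightly.

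**Working it through.** **The plan's own figures.** The plan states no power or sample size for ESA use. SAP 2.3 sizes the trial on the two primary endpoints. For duration of severe neutropenia (difference 2 days, SD 2.5, one-sided 0.0125, 90% power) a two-sample t test gives 89.9% at 40 per arm and 90.7% at 41, which reproduces the stated 82. The final size is 100/0.95 = 105.3, rounded up to 106, or 53 per arm. That is the size used below.

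**Inputs assumed, because the documents do not give them.**
- ESA rates: 21.6% placebo vs 5.7% trilaciclib, which are the RBC transfusion rates of the earlier first-line study (Protocol 4.3.1) used as a stand-in, and 25% vs 10% as a second case.
- Prognostic strength: odds ratio (OR) of 1 to 3 per SD lower baseline hemoglobin.
- Stratum shares: 14% ECOG 2 and 28% brain metastases.

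**Method.** Simulation of about 4,000 trials per row, modified Poisson with robust variance, treatment and two binary strata in both models, one-sided 0.025, no cycle offset. Trials with no events in an arm were set aside. The Monte Carlo error of each power figure is about √(0.6 × 0.4/4000) = 0.8 points.

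| Rates | OR per SD | Power without HGB | Power with HGB | Gain (points) | Empirical SE of log ratio |
|---|---|---|---|---|---|
| 21.6% vs 5.7% | 1.0 | 60.3% | 60.4% | 0.1 | 0.626 to 0.629 |
| | 1.5 | 60.9% | 61.3% | 0.4 | 0.622 to 0.623 |
| | 2.0 | 59.9% | 61.0% | 1.1 | 0.644 to 0.644 |
| | 3.0 | 61.8% | 66.9% | 5.1 | 0.632 to 0.626 |
| 25% vs 10% | 1.0 | 48.8% | 49.3% | 0.5 | 0.545 to 0.548 |
| | 1.5 | 48.2% | 48.8% | 0.6 | 0.541 to 0.540 |
| | 2.0 | 48.7% | 51.7% | 3.0 | 0.539 to 0.534 |
| | 3.0 | 48.6% | 54.6% | 6.0 | 0.544 to 0.530 |

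At 50 per arm and OR 2 the gains were of the same order: 56.1% to 58.0%, and 46.5% to 50.1%.

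**Cross-check on another scale.** On a logistic latent scale the correlation is ln(OR)/√(ln(OR)² + π²/3). OR 2 gives 0.693/√(0.480 + 3.290) = 0.36, and OR 3 gives 1.099/√(1.207 + 3.290) = 0.52. A separate simulation indexed by latent correlation, at 21.6% vs 5.7% and two-sided 0.05, gave 60.6% to 62.4% at 0.3, 60.0% to 65.9% at 0.5 and 59.5% to 72.9% at 0.7. The two approaches agree where they overlap. Nothing in the documents supports a link as strong as 0.7.

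**Is the gain real precision?** Only in part at low event rates. At OR 3 the empirical SE falls by 1 − 0.626/0.632 = 0.9% and by 1 − 0.530/0.544 = 2.6%, less than the power gain suggests. With 15% in both arms and OR 3, one-sided rejection under the null moved from 2.0% to 2.8% against a nominal 2.5%. Some of the extra power is therefore a less conservative test.

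**If ESA use is rare.** At an assumed 10% vs 3%, expected events are 53 × 0.10 + 53 × 0.03 = 6.9. Power among analysable trials is then about 9% to 14% either way, and the empirical SE does not improve (0.689 to 0.710).

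**The case against.** The strongest reply is that nothing here is an error. The SAP's general rule is: "The efficacy analyses will use the stratification factors as covariates in statistical models". Those factors stay in the ESA model. For supportive endpoints the protocol says: "The detailed derivation for these endpoints along with their analysis methods will be included in the SAPs". The negative binomial models for all-cause dose reductions and for MAHE carry no baseline count either, and dose reductions are a confirmatory hypothesis. ESA use is also discretionary, barred in Induction Cycle 1 and allowed for symptomatic anemia, and the entry limit truncates baseline hemoglobin. All of these weaken its link to the outcome.

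All of that stands. It makes the omission a choice within the SAP's discretion, and it limits the size of any benefit. It does not explain why the SAP's two anemia-treatment models differ.

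A reader might infer that the Grade 3/4 hematologic toxicity model has the same gap. The documents do not support that. SAP 5.1.3.3 states: "Hematologic toxicities events are defined as any cycle where any hematologic lab value occurs that meets the CTCAE toxicity grade criteria". This makes one pooled yes/no variable across lineages, so no single baseline count matches it. Matching counts would need lineage-specific models that the section does not specify, or four extra terms with about 106 patients.

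**Conclusion.** The ESA model omits a covariate that the SAP uses for its nearest neighbour and that the protocol's ESA wording makes plausibly prognostic. Adding it is a minor improvement in precision and consistency: about 0 to 3 power points for an OR of 1 to 2 per SD, about 5 to 6 at OR 3 (latent correlation about 0.5), and possibly none if ESA use is rare. These figures rest on assumed event rates and an assumed prognostic strength.

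Two stronger readings are tempting and are not supported. One is that the trial loses power as a matter of fact: ESA use is unpowered in this plan, and the loss is near zero if hemoglobin is weakly prognostic. The other is that the claim of benefit beyond neutrophils is weakened. The red-cell endpoint under multiplicity control is RBC transfusion on/after Week 5 (SAP 6.2.7.1.4), and its model already carries baseline hemoglobin. ESA use lies outside the five tested hypotheses, and leaving out a baseline covariate does not bias a randomised comparison.

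**What to change.** In SAP 6.2.7.2.5, state that the modified Poisson model for ESA administration includes baseline hemoglobin as a covariate, as the RBC transfusion model does, and keeps the stratification factors and the log number of induction cycles as offset. If the sponsor prefers no covariate, a sentence giving the reason would resolve the inconsistency. Leave the Grade 3/4 hematologic toxicity model as it is.

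The cost is one line in the SAP and one model term. Hemoglobin is measured at screening and on Day 1 of Cycle 1, so no new data are needed. The change should be made before unblinding, so that the covariate cannot appear to have been chosen from the results.
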